The ADCS-CGIC requires the assessor to consider a number of cognitive, functional, and behavioral areas prior to providing an overall “global” assessment of clinical change. It is performed by interviewing the patient to assess function and mental status and the informant, using a worksheet that comprehensively lists relevant symptoms potentially useful in judging clinically meaningful change, and allows for notes for future reference. Further details of the test can be found in Section 5.3.7.4 of the study protocol. The ADCS-CGIC will be administered on Screening (Baseline) and Day 14 of each treatment period. Scores range from 1 (marked improvement) to 7 (marked worsening), where 4 indicates no change. Summary statistics of scores at Day 14 will be presented. A mixed model with the score as the outcome, fixed effects for treatment sequence, period, timepoint (i.e., Day 14), disease type, and treatment, and subject as a random effect will be analyzed. LS mean, LS mean difference and its associated p-value will be reported. AR1 and CS covariance structures may be explored if there are convergence issues. The effect size will be estimated using Cohen’s D: difference in means / pooled SD.

All ADCS-CGIC data will be listed.

Color Trails Test (Select Sites Only)

The Color Trails Test consists of numbered circles printed with vivid pink or yellow backgrounds that are perceptible to color-blind individuals. For Part 1, the respondent uses a pencil to rapidly connect circles numbered 1-25 in sequence. For Part 2, the respondent rapidly connects numbered circles in sequence, but alternates between pink and yellow. The length of time to complete each trial is recorded. The Color Trails Test will be administered on Day -1 (Baseline), Day 7, and Day 14 of each treatment period at selected sites. Summary statistics of completion times for Part 1, Part 2, and their time difference and change from baseline will be presented. A mixed model with change from baseline as the outcome, baseline as a covariate, fixed effects for treatment sequence, period, timepoint (i.e., Day 7 and Day 14), disease type, and treatment, and subject as a random effect will be analyzed. LS mean, LS mean difference and its associated p-value will be reported. AR1 and CS covariance structures may be explored if there are convergence issues. The effect size will be estimated using Cohen’s D: difference in means / pooled SD.

A bar plot of the least square mean change of the Part 2 completion time with error bars of the standard error will be produced, separated by AD and PD.

All Color Trails Test data will be listed.

Montreal Cognitive Assessment (MoCA)

Details of MoCA are outlined in section 8.4 of this SAP. The MoCA will be collected at Screening (Baseline) and Day 14 of each treatment period. Summary statistics of the MoCA-MIS Score and MoCA Total Score and change from baseline will be presented. A mixed model with change from baseline as the outcome, baseline as a covariate, fixed effects for treatment sequence, period, timepoint (i.e., Day 14), disease type, and treatment, and subject as a random effect will be

analyzed. LS mean, LS mean difference and its associated p-value will be reported. AR1 and CS covariance structures may be explored if there are convergence issues. The effect size will be estimated using Cohen's D: difference in means / pooled SD. This analysis will be performed using AD and PD as subgroups, and again using AD-MCI, AD-MD, PD-MCI, and PD-MD as subgroups.

All MoCA data will be listed.

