8.8. Analysis of Secondary Endpoints

Differences between CST-2032+CST-107 and placebo in performance in cognitive tasks will be assessed using the FAS. For continuous endpoints, the difference is defined as CST-2032+CST-107 minus placebo except as defined in the SAP (e.g., for certain CANTAB test [PAL, RTI, and SSRT]). Comparisons may be made using a mixed model with factors for disease criteria, treatment, treatment sequence, subject nested in sequence (as a random effect), period, and baseline values as appropriate. Comparisons between treatments may also be compared using the paired t-test and/or nonparametric tests where appropriate and as specified in the SAP. These analyses will be conducted for all subjects in the study and also for each disease subset (PD/AD).

Secondary endpoints related to cognition, physiological symptoms, mood and will be summarized by disease criteria, treatment, treatment sequence and overall using the FAS. Select summaries may be repeated in the PPS. Comparisons between treatments will be performed similarly for all secondary endpoints. All data will be listed.

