7.3 Baseline and Post-Baseline Changes

Unless stated otherwise, baseline and post-baseline change values will be based on the following:

- Baseline will be based on the last non-missing value collected prior to or on the treatment start date and time. Post-baseline values will be those collected after the treatment start date and time.
- Change from baseline is defined as: value – baseline value.

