9.2 Secondary Endpoints and Analyses

The FAS will be used for all secondary endpoint analyses unless stated otherwise. All inferential analyses are exploratory in nature given that this study was not powered based on any statistical assumptions.

CANTAB

Cognition function is assessed using the following CANTAB tests:

- Reaction Time (RTI)
- Verbal Recall Memory (VRM)
- Adaptive Tracking Task (ATT)
- Paired Associates Learning Task (PAL)
- Stop Signal Task (SST)
- Delayed Verbal Recall

The cognitive assessments measured as part of the CANTAB tests will be administered on Day - 1 (Baseline), and 3 hours after dosing on Days 1, 7, and 14 of each treatment period. Summaries will be presented by disease type and treatment sequence.

There are eighteen key measures based on the Measures Description downloaded from the CANTAB portal and as described by Cambridge Cognition, which are:

- RTI Median Five-Choice Movement Time: The median time taken for a subject to release the response button and select the target stimulus after it flashed yellow on screen, measured in milliseconds. The measurement name for this parameter in the files downloaded from the CANTAB portal is RTIFMDMT.
- RTI Median Five-Choice Reaction Time: The median duration it took for a subject to release the response button after the presentation of a target stimulus, measured in milliseconds. The measurement name for this parameter in the files downloaded from the CANTAB portal is RTIFMDRT.
- PAL First Attempt Memory Score: The number of times a subject chose the correct box on their first attempt when recalling the pattern locations. The measurement name for this parameter in the files downloaded from the CANTAB portal is PALFAMS.
- PAL Number of Patterns Reached: The number of patterns presented to the subject on the last problem they reached. The measurement name for this parameter in the files downloaded from the CANTAB portal is PALNPR.
- PAL Total Errors (Adjusted): The number of times the subject chose the incorrect box for a stimulus on assessment problems (PALTE), plus an adjustment for the estimated number of

errors they would have made on any problems, attempts and recalls they did not reach. The measurement name for this parameter in the files downloaded from the CANTAB portal is PALTEA.

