- VRM Free Recall Distinct Stimuli Mean Errors – P1.1-1.3: For each recording of VRMFRDM, a new record will be derived as the value of VRMFRDM subtracted from 18. The parameter decode will be VRMFRDME.
- VRM Delayed Free Recall Distinct Stimuli Errors – P2.1: For each recording of VRMFR21D, a new record will be derived as the value of VRMFR21D subtracted from 18. The parameter decode will be VRMFR21E.
- VRM Delayed Recognition Total Correct Errors – P2.2: For each recording of VRMD22TC, a new record will be derived as the value of VRMD22TC subtracted from 36. The parameter decode will be VRMD22TE.

For all 21 parameters, observed values at each assessment and changes from baseline will be summarized using descriptive statistics on the FAS and PPS. In addition to the descriptive statistic summaries, for each parameter, a mixed effects model approach will be used to evaluate treatment effect. The model will include change from baseline as the dependent variable, baseline as a covariate, treatment sequence, period, timepoint (i.e., Day 1: 3 hrs post-dose, Day 7: 3 hrs post-dose, Day 14: 3 hrs post-dose), disease type, and treatment as fixed effects, and subject as a random effect. The least square means will be summarized, as well as the least square mean difference between treatments, where the corresponding p-value for this LS mean difference will be provided. If there are convergence issues, alternative covariance structures may be used including autoregressive of order 1 (AR1) and compound symmetry (CS). The effect size will be estimated using Cohen's D: difference in means / pooled SD. This analysis will be performed using AD and PD as subgroups, and again using AD-MCI, AD-MD, PD-MCI, and PD-MD as subgroups.

Additionally, using treatment period 1 and treatment period 2 data separately, all 21 parameters will have observed value and change from baseline summarized, and a mixed effects model with change from baseline as the dependent variable, baseline as a covariate, timepoint (i.e., Day 1: 3 hrs post-dose, Day 7: 3 hrs post-dose, Day 14: 3 hrs post-dose), disease type, and treatment as fixed effects, and subject as a random effect will be evaluated. The least square means, least

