The pVFTs will be administered on Day -1 (Baseline), Day 1, Day 7, and Day 14 of each treatment period. Summary statistics of observed values and change from baseline will be

presented. A mixed model with change from baseline as the outcome, baseline as a covariate, fixed effects for treatment sequence, period, timepoint (i.e., Day 1, Day 7, Day 14), disease type, and treatment, and subject as a random effect will be analyzed. LS mean, LS mean difference and its associated p-value will be reported. AR1 and CS covariance structures may be explored if there are convergence issues. The effect size will be estimated using Cohen's D: difference in means / pooled SD. This analysis will be performed using AD and PD as subgroups, and again using AD-MCI, AD-MD, PD-MCI, and PD-MD as subgroups. The analysis will be presented on the FAS and repeated on the PPS.

Bar plots of the least square mean change of Alphabet and Category scores with error bars of the standard error will be produced, separated by AD and PD.

All pVFT data will be listed.

Facial Expression Recognition Task (FERT)

Analyses of FERT data will be summarized in a separate analysis plan.

Digital Symbol Substitution Test (DSST)

The DSST will be administered on Day -1 (Baseline), Day 1, Day 7, and Day 14 of each treatment period. Summary statistics of the total score observed values and change from baseline will be presented. A mixed model with change from baseline as the outcome, baseline as a covariate, fixed effects for treatment sequence, period, timepoint (i.e., Day 7, Day 14), disease type, and treatment, and subject as a random effect will be analyzed. LS mean, LS mean difference and its associated p-value will be reported. AR1 and CS covariance structures may be explored if there are convergence issues. The effect size will be estimated using Cohen's D: difference in means / pooled SD. This analysis will be performed using AD and PD as subgroups, and again using AD-MCI, AD-MD, PD-MCI, and PD-MD as subgroups. The analysis will be presented on the FAS and repeated on the PPS.

A bar plot of the least square mean change of DSST total score with error bars of the standard error will be produced, separated by AD and PD.

All DSST data will be listed.

Geriatric Depression Scale – 30 questions (GDS-30)

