The GDS is a 30-item self-administered yes/no question test constructed for brief screening of depression in elderly persons. Total scores are the summation of scored responses (responses indicating worsening depression equate to 1, and responses indicating lessening depression equate to 0) from each question. Scores greater than 9 are considered suspect for depression. The GDS will be administered on Day -1 (Baseline), Day 1, and Day 14 of each treatment period. Summary statistics of total scores and change from baseline will be presented. A mixed model with change from baseline as the outcome, baseline as a covariate, fixed effects for treatment sequence, period, timepoint (i.e., Day 1, Day 14), disease type, and treatment, and subject as a random effect will be analyzed. LS mean, LS mean difference and its associated p-value will be

reported. AR1 and CS covariance structures may be explored if there are convergence issues. The effect size will be estimated using Cohen's D: difference in means / pooled SD.

All GDS data, included responses to individual questions, will be listed.

Conners Adult Attention Deficit Hyperactivity Disorder Scale (ADHD) Rating Scale, short form, self-report (CAARS)

The CAARS is a 26-item scale designed to assess, diagnose, and monitor treatment of attention deficit/hyperactivity disorder (ADHD) in adults. The self-report short form contains factor-derived scales for inattention/memory, hyperactivity/restlessness, impulsivity/emotional lability, and problems with self-concept. Individuals are asked to rate themselves on a range of symptoms and behaviors associated with ADHD as adults using a 4-point scale: 0=Not at all/never; 1=Just a little/once in a while; 2=Pretty much/often; 3=Very much/very frequently. The CAARS will be administered on Day -1 (Baseline), Day 1, and Day 14 of each treatment period. Total score will be derived as the sum of results from the 26 questions at each visit and can range from 0 to 78. Subscales will be derived as follows:

- Inattention/Memory Problems: sum of scores from questions 3, 5, 17, 18, and 21
- Hyperactivity/Restlessness: sum of scores from questions 4, 6, 10, 11, and 23
- Impulsivity/Emotional Lability: sum of scores from questions 1, 7, 8, 13, and 20
- Problems with Self-Concept: sum of scores from questions 9, 15, 16, 25, and 26
- ADHD Index: sum of scores from questions 2, 7, 8, 9, 11, 12, 14, 17, 19, 22, 24, and 26

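### The multi-visit crossover models name subject as the only random effect and use one baseline slope, so nominal 5% treatment tests would reject about 7–16% of the time under no effect

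*SAP*

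**What the plan says.** SAP 9.2 fits one mixed model to each CANTAB parameter over both periods. The outcome is change from baseline. Baseline is a covariate, and sequence, period and timepoint are fixed effects, followed by "Day 14: 3 hrs post-dose), disease type, and treatment as fixed effects, and subject as a random effect". Assessments are on Day -1 and then "3 hours after dosing on Days 1, 7, and 14 of each treatment period". Under SAP 7.3, "Baseline will be based on the last non-missing value collected prior to or on the treatment start date and time", so one baseline value serves every visit of a period.

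The same structure recurs:

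- **pVFT, three visits:** "timepoint (i.e., Day 1, Day 7, Day 14), disease type, and treatment, and subject as a random effect will be analyzed".
- **DSST, two visits:** "timepoint (i.e., Day 7, Day 14), disease type, and treatment, and subject as a random effect will be analyzed".
- **GDS-30, CAARS and SAS-6, two visits:** "timepoint (i.e., Day 1, Day 14), disease type, and treatment, and subject as a random effect will be analyzed".
- **Color Trails Test:** Days 7 and 14.
- **Z-scores (SAP 9.3):** three visits.

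The only text on covariance in 9.2 is conditional on convergence problems: "alternative covariance structures may be used including autoregressive of order 1 (AR1) and compound symmetry (CS". The z-score models in 9.3 carry no such sentence. No first-choice residual structure, no blocking unit and no degrees-of-freedom method is given.

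Protocol 8.8 lists "treatment sequence, subject nested in sequence (as a random effect), period, and baseline values as appropriate" in a model that has no timepoint factor.

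**The concern.** The protocol's random effect suits one value per subject and period. The SAP added repeated visits within each period but no term for what those visits have in common. Two things are then left out:

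1. **Subject-by-period variance.** A subject's good or bad fortnight is treated as independent visit error.
2. **Shared baseline noise.** All change scores in a period are taken from the same Day -1 value. One slope has to fit both the between-subject relation, which is strong, and the within-subject relation, which is weak. The compromise leaves baseline error in every visit of the period.

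Both make the model-based standard error of the treatment difference too small. Confidence intervals and p-values for cognition, mood, attention and apathy would look more precise than the data allow. SAP 6.1 sets a 5% level, and 9.2 promises a p-value for each of 21 CANTAB parameters. SAP 4.3 warns against over-reading a non-significant result, but nothing guards against standard errors that are too small.

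**Working it through.** **Inputs from the documents.** About 60 subjects (SAP 4.3), two periods, 1:1 sequences (4.2), K = 3 or 2 post-dose visits per period (9.2, 9.3), two-sided 5% (6.1). The plan has no figure of its own to reproduce.

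**Assumed, because the documents give no variances.** Y = S + P + e for subject, subject-by-period and visit. Baseline is one such value per period, B = S + P + e0. Variances s, p and v sum to 1, with v = 0.2–0.4 and p = 0–0.20. There is no treatment effect.

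**Algebra.** Modelling Y − B with slope g on B is the same as modelling Y with slope b = 1 + g. The part shared by all visits of a period is (1 − b)P − b·e0, with variance

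c = (1 − b)²p + b²v.

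- True variance behind the period contrast, per-visit scale: T = v + Kc.
- Residual variance the model uses. Of 2K − 1 within-subject degrees of freedom, one carries T and the rest carry v: M = v + Kc/(2K − 1).
- True SD / model SE = √(T/M). Rejection rate = P(|Z| > 1.96/√(T/M)).

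The slope b is a weighted average of the within-subject slope p/(p + v) and the between-subject slope (s + p/2)/(s + (p + v)/2). The weights are K(p + v)/M and 2K(s + (p + v)/2)/V, where V = 2K[(1 − b)²(s + p/2) + v/(2K) + b²v/2]. Solve by iteration.

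**Example 1: K = 3, s = 0.7, p = 0, v = 0.3.** The slopes are 0 and 0.7/0.85 = 0.824.

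- At b = 0.404, M = 0.329 and V = 1.94. The weights are 0.9/0.329 = 2.73 and 5.1/1.94 = 2.63, which return b = 0.404.
- c = 0.404² × 0.3 = 0.049. T = 0.3 + 3(0.049) = 0.447.
- √(0.447/0.329) = 1.165, so the rejection rate is 9.2%. Simulation gave 9.5%.

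**Example 2: K = 3, s = 0.6, p = 0.1, v = 0.3.** The slopes are 0.25 and 0.8125, so b = 0.538.

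- c = 0.0213 + 0.0868 = 0.108. T = 0.624 and M = 0.365.
- The ratio is 1.31 and the rejection rate 13.4%. Simulation gave 12.5%.
- Splitting the baseline but keeping subject as the only random effect sets b = 0.25. Then c = 0.0563 + 0.0188 = 0.075, T = 0.525, M = 0.345, the ratio is 1.23 and the rejection rate 11.2%. Simulation gave 10.7%. The split alone is not enough when p > 0.

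**Full simulation.** REML, N = 60 with 30 per sequence, 5,000 runs per cell, Monte Carlo SE 0.3–0.5 points. Rejection (%) of the model as written, at v = 0.2 / 0.3 / 0.4:

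| p | Three visits | Two visits |
|---|---|---|
| 0 | 11.0 / 9.5 / 8.2 | 10.9 / 9.2 / 6.9 |
| 0.05 | 14.4 / 12.0 / 10.3 | 11.5 / 9.4 / 8.5 |
| 0.10 | 15.2 / 12.5 / 11.2 | 11.5 / 9.4 / 9.2 |
| 0.20 | 16.4 / 14.5 / 13.8 | 12.5 / 11.3 / 9.7 |

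True SD / model SE was 1.13–1.42 (three visits) and 1.10–1.26 (two). Mean estimates stayed within 0.003 of zero.

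**Remedies on the same grid:**

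| Model | Rejection |
|---|---|
| As written, Kenward-Roger added | changes by at most 0.1 point |
| Split baseline only, p = 0 | 4.5–5.4% |
| Split baseline only, p = 0.05–0.20 | 7.9–15.4% (three visits), 6.5–10.5% (two) |
| Subject-by-period term only | 4.4–5.6% |
| Both | 3.8–5.3% |

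With both changes the true SD of the estimate is 2–28% below the model as written. For Example 1 the formula √(2(c + v/K)/N) gives √(2 × 0.149/60) = 0.070 as written. With both changes c = 0, and it gives √(2 × 0.1/60) = 0.058.

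**The named fallbacks.** Compound symmetry blocked by subject is the same covariance as a random subject effect, so it changes nothing. For K = 3, v = 0.3 and random subject kept (500 runs), AR1 within period rejected 7.0–8.4%, and AR1 across all six visits 8.6–11.4%.

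**The case against.** The strongest reply is that the SAP may intend something better. The word for alternative structures implies a primary one, and an unstructured default is a natural reading. If so, there is little or no inflation. Unstructured within period with random subject gave 5.0–5.6%, and a 6×6 matrix by subject gave 4.4–6.8% (250 runs, Monte Carlo SE about 1.5 points). On that view the secure fault is under-specification. But no default is written, the 9.3 models have no covariance sentence, and the text that is there specifies subject alone. Naming the structure is the remedy either way.

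Other points carry some weight:

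- **The range depends on assumed variances.** A wider grid gave 6.2% (s = v = 0.5, p = 0) up to 23% in extreme settings. It was above 5% in every setting tried.
- **Z-score models keep only subjects with baseline z below -0.5.** An illustrative restricted run gave 5.9–9.5% at p = 0 and 12.6–14.3% at p = 0.1. Inflation persists, but the 8.2% lower bound does not carry over.
- **DSST may be a slip.** The test is also given on Day 1, and the 9.3 DSST model lists three visits, while 9.2 lists two. It is treated here as written.
- **The baseline split is not needed for validity** once the subject-by-period term is in. That is correct; the split recovers efficiency.
- **The inference is exploratory, with no type I error control.** That limits the consequence but does not make the standard errors right.

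**Conclusion.** The concern holds: the models are wrong as written. Under the stated variance assumptions, nominal 5% tests reject 8.2–16.4% of the time with three visits and 6.9–12.5% with two. At assumed subgroup sizes of 30 and 16 the range is 8.5–15.6%. The size rests on variances the documents do not give; the direction did not change in any setting.

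Three-visit models affected: CANTAB, pVFT and the z-scores. Two-visit models affected: raw DSST, GDS-30, CAARS, SAS-6 and Color Trails. Not affected: the separate Period 1 and Period 2 CANTAB models, and the one-visit endpoints (MoCA, ADCS-CGIC). The primary endpoint is safety and the estimates are unbiased, so this should be fixed before database lock but does not threaten the trial's main purpose.

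**What to change.** State in every multi-visit crossover model of SAP 9.2 and 9.3:

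> Random effects are subject and subject-by-period; degrees of freedom are by Kenward-Roger. Baseline enters as two covariates: the subject's mean baseline over the periods observed, and the period-specific deviation from that mean.

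An acceptable alternative for the random part is random subject plus an unstructured residual covariance blocked by subject within period. Do not split the baseline without one of these.

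Fallbacks on non-convergence, always keeping random subject:

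- Compound symmetry blocked by subject within period replaces the subject-by-period intercept and must not be combined with it.
- With three visits, use AR1 within period only together with that intercept (5.2–5.4% with one slope, 3.6–4.6% with the split; 500 runs).
- With two visits, AR1 within period is the same structure as compound symmetry, so the first rule applies.

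**Cost.** Two sentences of text, one random term and two derived covariates per model; no new data. The random term alone widens confidence intervals by 22–55% (three visits) or 16–31% (two). With the split as well, the change is -2% to +39% or -8% to +22%, so some endpoints will lose nominal significance. The subject-by-period variance may be estimated at zero: in about half of runs when it is truly zero, and when it is 0.1–0.2 in 1–13% of runs (N = 30) or 6–22% (N = 16). Type I error stayed at 3.8–5.5% in those small-sample cells.

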- CANTAB, pVFT and DSST to be administered on Days 1, 7 and 14 of each treatment period:
 - 3 ± 0.5 hours after administration of study drug. Tests should be conducted at approximately the same time of day (± 1 hour) and under the same food status on Days -1, 1, 7 and 14.

15 SAS-6, CAARS, and GDS-30 are per subject self-report. These tests will be administered at the following timepoints in each treatment period:

- Day -1: Prior to administration of CST-107 or matching placebo
- Day 1: at least 2 hours after dosing of study drug,
- Day 14: at least 2 hours after dosing of study drug.

16 C-SSRS not completed on Day -1 during Treatment Period 1.

17 The ADCS-CGIC will be administered at the following timepoints in each treatment period:

- Screening
- Day 14: at least 3 hours after dosing of study drug.

18 On Day -1 only, CST-107 or matching placebo is to be administered upon completion of all scheduled study assessments. On all other dosing days, study drugs (CST-2032+CST-107 or matching placebos) are to be co-administered. On Days -1, 1, 7 and 14 the study drugs are administered in the clinic.

19 On Day 1, safety labs will be collected pre-dose and approximately 4 hours post-dose (chemistry only at 4 hours post-dose).

20 On Days 7 and 14, safety labs will be collected approximately 4 hours post-dose.

21 Inclusion/exclusion criteria not re-assessed on Day -1 of Treatment Period 2.

LIST OF ABBREVIATIONS

Abbreviation	Definition
ADCS-CGIC	Alzheimer's Disease Cooperative Study-Clinical Global Impression of Change
APOE4	Apolipoprotein E4
β-AR	Beta-adrenoceptor
β-hCG	Beta human chorionic gonadotropin
AD	Alzheimer's Disease
AE	Adverse event
ADHD	Attention Deficit/Hyperactivity Disorder
AS	Apathy scale
ASL MRI	Arterial spin labelling magnetic resonance imaging
ATT	Adaptive tracking test
AUC _{inf}	Area under the drug concentration-time curve from time zero to infinity
AUC _t	Area under the drug concentration-time curve from time zero to time t
BMI	Body mass index
BP	Blood pressure
CAARS	Connors Adult Attention Deficit/Hyperactivity Disorder Scale – short form, self-report
cAMP	cyclic adenosine monophosphate
CANTAB	Cambridge Neuropsychological Test Automated Battery
CBF	Cerebral blood flow
cGCP	Current Good Clinical Practice
CLIN-002	CST103/CST107/CST109-CLIN-002
CLIN-007	CST2032-CLIN-007
Cmax	Maximum concentration
CNR	Contrast-to-noise ratio
CNS	Central nervous system
CRF	Case report form
CST-107	Nadolol
DSMB	Data and Safety Monitoring Board

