Summary statistics of z-scores and change from baseline for subjects with a baseline deficit will be presented for each of the 5 CANTAB parameters marked. Baseline deficit is defined as having a baseline z-score less than -0.5. Subjects with baseline values greater than or equal to -0.5 will not be summarized. Additionally, a mixed model approach will be used to evaluate treatment effect. The model will include change from baseline in z-score as the dependent variable, baseline as a covariate, treatment sequence, period, timepoint (i.e., Day 1: 3 hrs post-

hose, Day 7: 3 hrs post-dose, Day 14: 3 hrs post-dose), disease type, and treatment as fixed effects, and subject as a random effect. The least square means will be summarized, as well as the least square mean difference between treatments, where the corresponding p-value for this LS mean difference will be provided.

Summary statistics of z-scores and change from baseline for subjects with a baseline deficit for the two pVFT parameters will also be presented. Baseline deficit is defined as having a baseline z-score less than -0.5, and subjects with baseline values greater than or equal to -0.5 will not be summarized. Additionally, a mixed model with z-score change from baseline as the dependent variable, baseline as a covariate, treatment sequence, period, timepoint (i.e., Day 1, Day 7, Day 14), disease type, and treatment as fixed effects, and subject as a random effect will be analyzed, with the least square means, least square mean difference, and corresponding p-value will be provided.

Summary statistics of z-scores and change from baseline for subjects with a baseline deficit for DSST total score will be presented. Baseline deficit is defined as having a baseline z-score less than -0.5, and subjects with baseline values greater than or equal to -0.5 will not be summarized. Additionally, a mixed model with z-score change from baseline as the dependent variable, baseline as a covariate, treatment sequence, period, timepoint (i.e., Day 1, Day 7, Day 14), disease type, and treatment as fixed effects, and subject as a random effect will be analyzed, with the least square means, least square mean difference, and corresponding p-value will be provided.

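### The DSST mixed model lists only Days 7 and 14 although DSST is also collected on Day 1, so it omits a third of the post-dose data and disagrees with the SAP's own DSST z-score model

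*SAP*

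**What the plan says.** The DSST paragraph of SAP 9.2 first sets the schedule: "The DSST will be administered on Day -1 (Baseline), Day 1, Day 7, and Day 14 of each treatment period". The Protocol's Schedule of Events (footnote 14) agrees: "CANTAB, pVFT and DSST to be administered on Days 1, 7 and 14 of each treatment period". SAP Appendix 2 repeats that footnote.

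The same SAP paragraph then specifies a mixed model for change from baseline, with baseline as covariate, subject as random effect and "fixed effects for treatment sequence, period, timepoint (i.e., Day 7, Day 14), disease type, and treatment". Its least-squares mean difference and p-value are reported, with a plot of the least-squares mean changes. The analysis is run for AD and PD, run again for the four disease-by-severity groups, and repeated on the Per-Protocol Set.

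The verbal fluency model in SAP 9.2 has "fixed effects for treatment sequence, period, timepoint (i.e., Day 1, Day 7, Day 14), disease type, and treatment". In SAP 9.3 the DSST returns as a z-score ("Summary statistics of z-scores and change from baseline for subjects with a baseline deficit for DSST total score will be presented"), with a model containing "baseline as a covariate, treatment sequence, period, timepoint (i.e., Day 1, Day 7, Day 14), disease type, and treatment as fixed effects".

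**The concern.** The SAP gives two timepoint lists for one test, and the shorter one contradicts the collection schedule stated two sentences earlier. The model has main effects for treatment and timepoint and no interaction between them, so the reported treatment difference is an average over the days listed. The list therefore decides what is estimated as well as how much data is used.

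Read literally, the DSST effect covers Days 7 and 14, while the CANTAB and verbal fluency effects from the same visits cover Days 1, 7 and 14. Day 1 follows the first CST-2032 dose and the later days follow repeated dosing. If those effects differ, the DSST could diverge from the other tests simply because different days were averaged. Left unresolved, the conflict also lets the two-day or three-day version be chosen at programming, in a study with no multiplicity adjustment (SAP 6.4).

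**Working it through.** **Step 1: compare the lists.** Collection days and model timepoints in SAP 9.2, with the DSST z-score model of SAP 9.3 added:

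| Test | Post-dose collection days | Days in model | Match |
|---|---|---|---|
| CANTAB | 1, 7, 14 | 1, 7, 14 | yes |
| Verbal fluency | 1, 7, 14 | 1, 7, 14 | yes |
| **DSST (9.2)** | **1, 7, 14** | **7, 14** | **no** |
| DSST z-score (9.3) | 1, 7, 14 | 1, 7, 14 | yes |
| GDS-30, CAARS, SAS-6 | 1, 14 | 1, 14 | yes |
| Color Trails | 7, 14 | 7, 14 | yes |
| ADCS-CGIC, MoCA | 14 | 14 | yes |

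The DSST model in 9.2 is the only mismatch. SAP 2.1, on changes to the planned analysis, speaks only of Type I error and hypothesis ordering. Protocol 8.8.1 groups DSST with CANTAB and verbal fluency and restricts no days.

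**Step 2: count the records.** Inputs are about 60 subjects (SAP 4.3), 2 periods and 3 scheduled post-dose visits per period, assuming complete data.

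- All visits: 60 × 2 × 3 = 360
- As modelled: 60 × 2 × 2 = 240
- Omitted: 360 − 240 = 120, and 120/360 = 33.3%

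**Step 3: cost in precision.** Let ρ be the correlation, across visits, of a subject's active-minus-placebo differences, assumed equal for every pair of visits. The variance of a mean over m visits is proportional to [1 + (m − 1)ρ]/m, so the ratio of standard errors, two visits to three, is

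sqrt{[(1 + ρ)/2] / [(1 + 2ρ)/3]}

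The documents give no value for ρ, so all values below are assumptions.

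| ρ | (1 + ρ)/2 | (1 + 2ρ)/3 | SE ratio |
|---|---|---|---|
| 0 | 0.500 | 0.333 | 1.22 |
| 0.2 | 0.600 | 0.467 | 1.13 |
| 0.4 | 0.700 | 0.600 | 1.08 |
| 0.6 | 0.800 | 0.733 | 1.04 |
| 0.9 | 0.950 | 0.933 | 1.01 |

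Over 0.2 to 0.6 the standard error rises by 13% down to 4%; the outer rows give limits of about 22% and 1%. The plan states no power calculation, so there is no figure of its own to reproduce.

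**The case against.** The best reply is that this is a drafting slip. The omission sits in one parenthesis and no sentence excludes Day 1. The same two-day list is correct for Color Trails, which is not done on Day 1, so copied text is plausible. SAP 7.5 makes nominal visits the basis of analysis, and a programmer might include Day 1 regardless. The documents do not show which was intended. But the parenthesis is the only definition of the model's timepoints, so a slip there is still a wrong rule if followed.

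Several limits do stand:

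- Color Trails and MoCA are also modelled on other days, so the mismatch in estimand is with CANTAB and verbal fluency, not with every cognitive measure.
- The z-score model covers only subjects with a baseline z-score below −0.5, so aligning the days would not make the two DSST analyses identical. It would remove the unexplained difference in days.
- A third of the records is not a third of the information. Changes from a shared baseline tend to be positively correlated, which favours the smaller losses in the table.
- The precision comparison presumes the same treatment effect at each visit. If Day 1 differs, adding it changes the target as well as the precision.
- The descriptive summaries are not restricted to two days, and all DSST data will be listed.
- All inference is called exploratory (SAP 9), and the primary endpoint is safety.

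**Conclusion.** The inconsistency is real and the model is wrong as written. The omission of one post-dose visit in three follows directly from the SAP's own text. The change in what is estimated, relative to CANTAB and verbal fluency, needs no assumption either. The 4% to 13% loss of precision depends on an assumed correlation of 0.6 to 0.2, equal across pairs of visits. The study is described in SAP 4.3 as underpowered for meaningful cognitive benefit, so collected data should not be left out of a model without a stated reason. Because the endpoint is secondary and exploratory, this is a correction that should be made; it does not threaten the trial's main conclusion.

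**What to change.** In the DSST paragraph of SAP 9.2, change the model's timepoint list to Day 1, Day 7, Day 14, matching the verbal fluency model and the DSST z-score model in SAP 9.3. If the two-day restriction was intended, the SAP should instead give the reason and reconcile the z-score model with it. Either way, settle it before unblinding; SAP 2 allows the final version up to database lock. The cost is one phrase. The Day 1 data are already scheduled, and any program already written to the two-day list would need only its visit selection changed.
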